4.3. Sample size

Data obtained from the PAANTHER study showed that the TB prevalence was 57.3% in HIVinfected children with presumptive TB as defined per standard algorithm entry criteria, with a proportion of 39.3% of children being on ART. We expect a higher proportion of children on ART in this new study, reaching 50%, and a resulting lower prevalence of TB, around 50%, based on improved accesss to HIV care in our study settings.

With an algorithm sensitivity and specificity of 89% and 61%, respectively, the proportion of missed TB cases among children not started on treatment based on the PAANTHER algorithm (assessed by the TB incident cases in the 6 months period after applying the algorithm) is estimated to 15%, which corresponds to a negative predictive value (NPV) of 85%. For sample size calculations, we used this expected NPV of 85% and an unacceptable NPV of 75% (minimal acceptable 95% lower confidence interval limit), a one-sided test of level 5% and a probability β =5%, which results in a sample of 176 children not-initiated on treatment as per

the PAANTHER TB treatment decision algorithm and a total sample of 550 children, taking into account an expected 10% of missing data [63].

4.4. Provisional study timeline

- First inclusion: 4th quarter 2019
- Inclusion period: 27 months
- Duration of follow-up for each participant once enrolled: 6 months
- Enrolment stop due to Covid-19 pandemic: April 1st, 2020
- Progressive enrolment restart: June-December 2020
- Last visit of the last patient: 2nd quarter 2022
- Overall duration of the study (from the first inclusion to the last visit): 33 months

4.5. Cost-effectiveness ancillary study

A cost-effectiveness study will be performed as part of the TB-Speed Project Output 5 ("Evaluation of cost-effectiveness of the proposed diagnostic approaches"). Cost-effectiveness and budget impact analyses will evaluate the incremental cost-effectiveness ratio (ICER) and the long-term impact of improving TB diagnostics in children with HIV, guide health authorities' decisions and support the implementation of the TB-Speed approach in resource-limited settings.

A mathematical model will be developed to project health-economic outcomes including TB cases and mortality in children with HIV. The model will be developed in collaboration with ScHARR of the University of Sheffield (UK) and the CaP-TB project (see Chapter 11.2.4).

The cost-effectiveness analysis will be from the health payer perspective and only direct health care costs will be included. A budget impact analysis will be conducted to evaluate the actual impact of implementing the TB-Speed approach on healthcare budgets at 2- and 5-year horizons in the countries participating in TB-Speed.

A separate analysis plan will be written for the cost-effectiveness analysis. Data collection methods for cost data are outlined in Chapter 10.1.2.

5. STUDY ENROLLMENT

5.1. Study population

5.1.1. Inclusion criteria

- 1. Children aged 1 month to 14 years
- 2. Documented HIV-infection (i.e., confirmed before entry into the study)
- 3. Presumptive TB based on at least one criteria among the following¹:
 - a. Persistent cough for more than 2 weeks
 - b. Persistent fever for more than 2 weeks
 - c. Recent failure to thrive (documented clear deviation from a previous growth trajectory in the last 3 months or Z score weight/age < 2)
 - d. Failure of broad spectrum antibiotics for treatment of pneumonia
 - e. Suggestive CXR features

OR

History of contact with a TB case and any of the symptoms listed under point 3 with a shorter duration (< 2 weeks)

¹ PAANTHER inclusion criteria

4. Informed consent signed by parent/guardian

5.1.2. Non-inclusion criteria

1. Ongoing TB treatment or history of intake of anti-TB drugs in the last 3 months (isoniazid alone or rifampin/isoniazid for preventive therapy is not an exclusion criteria)

5.2. Recruitment sites

The study will be implemented at HIV inpatient/outpatient centres from 7 selected hospitals in four African countries where TB incidence and paediatric HIV prevalence are likely to vary: Côte d'Ivoire, Mozambique, Uganda, and Zambia (see Table 1). All participating hospitals are University Teaching Hospitals (UTH) or equivalent in terms of level of care, including national or regional reference hospitals collaborating with the TB-Speed Pneumonia and TB-Speed HIV studies (see Appendix 3).

Table 3 presents indicative recruitment capacities of participating hospitals, based on a capacity assessment questionnaire including the number of children <15 years followed up in HIV treatment and care centres in 2016 and 2017.

| Country | Nb sites | Hospitals | Paediatric HIV active file |
|---------------|----------|---|----------------------------|
| Côte d'Ivoire | 2 | Cocody UTH, Abidjan | 347 |
| | | Treichville UTH, Abidjan | 460 |
| Uganda | 1 | Regional reference Hospital, Mbarara | 800 |
| Mozambique | 2 | Maputo Central Hospital, Maputo | 700 |
| | | José Macamo General Hospital, Maputo | 240 |
| Zambia | 2 | Lusaka University Teaching Hospital, Lusaka | 2 413 |
| | | Arthur Davidson Children Hospital, Ndola | 2 863 |

Table 3: Study sites from participating countries

6. STUDY INTERVENTIONS

6.1. Diagnostic procedure evaluated

The PAANTHER algorithm and prediction score was designed as a guiding tool for empirical TB treatment decision in HIV-infected children with presumptive TB (see Figure 1 below and Appendix 2). The proposed score includes:

- History of close contact with a smear+ TB case
- Suggestive TB symptoms (prolonged fever, unremitting cough, hemoptysis, weight loss in the past 4 weeks)
- Tachycardia
- Chest radiography features (miliary, alveolar opacities, lymph nodes)
- Abdominal ultrasound features (abdominal lymphadenopathy)
- Xpert MTB/RIF assay which will be replaced by Ultra

Points scored by each sign or symptom is shown in the table below.

| Exam/assessment | Features/items | Points | |
|----------------------|---|--------|--|
| Contact history | History of contact with a smear + TB case | 118 | |
| Symptoms | Fever lasting > 2 weeks | 66 | |
| | Unremitting cough | 39 | |
| | Hemoptysis in previous 4 weeks | 79 | |
| | Weight loss in previous 4 weeks | 24 | |
| Clinical signs | Tachyardia | 54 | |
| Xpert MTB/RIF Ultra | Positive Xpert MTB/RIF Ultra result | 241 | |
| Chest radiography | Miliary | 90 | |
| | Alveolar opacity | 74 | |
| | Lymph nodes | 100 | |
| Abdominal ultrasound | Abdominal lymph nodes | 73 | |

Table 4: PAANTHER TB treatment decision algorithm components and point scoring

[figure not shown]

Figure 1: Implementation of the PAANTHER TB treatment decision algorithm in the context of the TB-Speed study

A score of >100 is highly predictive of TB. In children with a score >100, anti-TB treatment will be initiated immediately. In children with a score of <100, TB treatment will not be initiated except in those with severe/life-threatening conditions for whom TB treatment decision could be made at the discretion of the site clinician. TB could be definitely ruled out after further assessment and decision made as to what treatment the children should receive in accordance with existing national protocols, along with clinical follow-up.

6.2. Capacity building

Implementation of the TB-Speed HIV study will include a preparation and capacity building phase conducted at participating hospitals, which are tertiary level reference and university teaching hospitals also involved in the TB-Speed Pneumonia study in Zambia and Uganda. Sites which are not already equipped will be provided with digital radiography (DR) plates for digital CXR, ultrasound machine, and sample collection material (including battery-operated suction machines for NPA collection). Laboratories will be equipped with GeneXpert devices if not available through National Programs as well as -80°C freezers for biobanking.

Specific training will be provided to site investigators and hospital staff in HIV outpatient/inpatients centres (doctors and nurses) on TB diagnosis, study procedures, and Good Clinical Practice (GCP). Initial training will be provided onsite by the study central coordinating team. Based on didactic and practical presentation, trainings will include the following topics:

- Childhood TB diagnosis and management
- Clinical follow-up (eligibility criteria, informed consent process, patient schedule, TB assessment, management in the case of AE/SAEs)
- Biological samples collection (NPA) and laboratory procedures including biobanking
- Use of DR plates
- Non-routine TB assessment procedures and their interpretation (MLR, CRP, abdominal echography)
- Use of the PAANTHER treatment decision score
- Data collection and use of electronic Case Report Form (eCRF)
- Data management and monitoring

6.3. Implementation at site level

The TB-Speed HIV study will be implemented in 7 tertiary healthcare level hospitals in main cities of Côte d'Ivoire, Uganda, Mozambique, and Zambia (see Table 1 and Table 3). A total of 550 HIV-infected children (aged < 15 years) with clinically suspected TB (presumptive TB) will be enrolled, using standard inclusion criteria. The inclusion period will last until the expected number of children is reached, but recruitment by study site will however not be capped. This could be achieved in about 27 months based on estimated recruitment capacities of participating sites (see Chapter 5.2) and the overall delay incurred by the study, in particular due to the Covid-19 pandemic.

6.4. Study flow chart

[figure not shown]

Figure 2: TB-Speed HIV study flow chart

¹Includes CXR features on CXR possibly performed in previous assessment of acute cough or fever ²Includes CXR features on CXR performed previously or specifically for the score ³Includes children with score <100 initiated on TB treatment by the clinician on the basis of severe/lifethreatening condition at D0

7. STUDY PROCEDURES

Recruitment will be performed at entry in HIV outpatient/inpatient centres of participating hospitals, as well as during the follow up of HIV-infected children on ART.

7.1. Selection process

Children will be first pre-screened for TB by attending clinicians and nurses in the context of routine care based on WHO criteria, i.e. with any one of the following symptoms: poor weight gain, fever, current cough and contact with a TB case [15]. If not routinely performed, this prescreening step will be reinforced and a screening logbook will be set up (if not already in place) to collect aggregated data on the eligibility criteria assessment process. Children pre-screened positive for TB will be further subjected to the study selection criteria by the study nurses.

Assessment for eligibility will be detailed in specific clinical SOPs. Children assessed as not having eligibility (presumptive TB) criteria may undergo a CXR and receive a broad spectrum antibiotic course as part of routine care and be reassessed later.

7.2. Informed consent and assent from children

The informed consent and assent process will be implemented by the study nurses following specific SOPs. They will ensure that parent(s)/guardian(s) and children over 7 years old have read and understood the content of the information sheets, and that they have received answers to all their questions before signing the informed consent. Written informed consent should be obtained prior to any study-specific clinical, biological or radiological exam.

The purpose, the nature of constraints and the foreseeable risks and benefits of the trial will be fully explained to the parent(s)/guardian(s) of eligible children. Importance of follow-up, especially in the case of children not initiated on treatment as per the PAANTHER TB treatment decision algorithm, will be emphasized. Parent(s)/guardian(s) will be informed that participation is voluntary and that they will be free to withdraw from the trial at any moment without justification or without any negative consequences for the quality of care and follow-up provided to their child. In addition to oral explanations, a written information sheet will be systematically provided (see Appendix 6). Documents with pictures will be available to help the parents and children to better understand the exams proposed in the study.

Children aged over 7 years are unable to consent but their assent should be obtained using age-appropriate information [64]. Separate information sheets and assent forms will be used to explain the purpose, the risks and benefits of the study. Whenever possible, a written confirmation will be obtained from the child. Consent should be obtained from the parent(s)/guardian(s) before assent is sought from the child [64]. If the child's assent is not collected, this will be recorded in the consent form with the reasons.

If the participation agreement is given by the parent(s)/guardian(s) and child if over 7 years old, the consent forms will be completed, signed and dated by the parent(s)/guardian(s), the child whenever possible and the study nurses or site investigators. Oral consent in the presence of a witness (not from the medical team) is acceptable in the case of illiteracy. The consent form will include separate consent for frozen samples conservation.

Agreement of one parent/guardian only is needed for participation but if one of the parent(s)/guardian(s) refuses the child's participation, the child will not be enrolled. Consent must represent the child's presumed will, and may be revoked at any time without detriment to the child. The explicit wish of a child to refuse participation or to be withdrawn from the study should be considered at any time. In this case, children will be referred for routine standard of care.

A copy of the signed consent(s) will be given to parent(s)/guardian(s). The original(s) consent(s) form will be retained by the site investigator in a safe place inaccessible to others, even when moving, throughout the study period and for 15 years after its end.

In the absence of national regulation, a person who usually assumes responsibility for the child's custody, care, and maintenance even though no court order exists formally appointing the person as the guardian, custodian, or adoptive parent of the child, will be considered as a guardian. Should any of the child's parents be alive but not living with the child, the usual caregiver will be considered as a guardian.

7.3. Patient schedule

| | Protocol visit | | | | | | | |
|---|----------------|-------|---------------------------------------|-------------------------------|-----------------------------|-----------------------------|-----------------------------|-----------------------------|
| | D0 | D1-D2 | D7 ¹ (+/- 1 day) | D15 (+/- 2 days) | Month 1 (+/- 2 weeks) | Month 2 (+/- 2 weeks) | Month 3 (+/- 2 weeks) | Month 6 (+/- 2 weeks) |
| Eligibility criteria | Х | | | | | | | |
| Informed consent(s) | х | | | | | | | |
| Clinical evaluation | х | | Х | Х | Х | Х | Х | Х |
| Medical history | Х | | Х | Х | Х | Х | Х | Х |
| Abdominal Ultrasonography | Х | | | | | | | |
| CXR | Х | | (X) ⁴ | (X) ⁴ | (X) ⁴ | Х | (X) ⁴ | Х |
| TB treatment decision algorithm scoring ² | х | х | | | | | | |
| TB treatment (if required) | Х | Х | Х | Х | Х | Х | Х | Х |
| TB drug adherence assessment | | | Х | Х | Х | Х | Х | Х |
| TB treatment response | | | Х | Х | Х | Х | х | Х |
| LTBI treatment (IPT or RH 3 Mo) ³ | | Х | Х | Х | Х | Х | Х | Х |
| Treatment and care of co- morbidities if needed | х | х | Х | Х | | | | |
| Lab assessment: | | | | | | | | |
| - Complete blood count (CBC) | Х | | | | | Х | | Х |
| - Transaminases and CRP | Х | | | | | Х | | Х |
| - CD4 count | Х | | | | | | | Х |
| NPA | Х | | | | | | | |
| Stool sample | Х | | | | | | | |
| Two GAs or expectorated sputum | | Х | (X) ⁴ | (X) ⁴ | (X) ⁴ | (X) ⁴ | (X) ⁴ | |
| Xpert MTB/RIF Ultra | Х | Х | (X) ⁴ | (X) ⁴ | (X) ⁴ | (X) ⁴ | (X) ⁴ | |
| Mycobacterial culture ⁵ | | Х | (X) ⁴ | (X) ⁴ | (X) ⁴ | (X) ⁴ | (X) ⁴ | |
| NPA safety and tolerability | Х | | | | | | | |
| Biobank (frozen samples): | | | | | | | | |
| - Whole blood | х | | | | | | | |
| - Plasma | Х | | | | | | | |
| - Urine | Х | | | | | | | |
| NPA, sputum and stool leftovers | х | | | | | | | |
| Maximum number of tubes collected ⁶ | 5 | | | | | 2 | | 3 |
| Maximum volume of blood collected ⁷ | 10.5 mL | | | | | 4 mL | | 6 mL |

- (1) Day 7 visit is performed only in children not initiated on TB treatment as per the PAANTHER treatment decision algorithm
- (2) TB treatment decision using the algorithm is taken as soon as the individual score is >100, or once the final score remains <100 and all tests have been performed

- (3) In those not initiated on treatment as per PAANTHER TB treatment decision algorithm
- (4) Performed in children with TB excluded by the algorithm, not improving or deteriorating clinically during followup
- (5) Performed on two GAs or 2 expectorated sputum
- (6) 2 mL of whole blood collected on heparin tubes for transaminases and CRP; 3 x 2 mL collected on EDTA tubes for CBC, CD4 count, and plasma biobank; 2.5 mL collected on PAXgene Blood RNA tubes for whole blood biobank. In children <18 months weighing <5 kg or children presenting with signs of severe anaemia (conjunctival or palmar pallor), plasma sample for biobank will not be collected

- (7) Volume of blood draw must not exceed 3 ml/kg/visit and 7 ml/kg/6 weeks

7.4. Inclusion visit

The following procedures will be performed during the inclusion visit (Day 0 to Day 2):

• Complete clinical evaluation

- Demographic information
 - Interview of parent/guardian and child on:
 - \circ History and duration of symptoms including fever, cough, weight loss
 - History of household TB contact
 - o History of past and current medication, including TB treatment and ART
 - History of chronic diseases and concomitant opportunistic infections
 - \circ BCG immunization
- Vital signs: respiratory rate, heart rate, temperature, weight, height, oxygen saturation
- Physical examination including respiratory system exam, adenopathy, hepatosplenomegaly, assessment of nutritional status
- Evaluation of the WHO clinical stage of HIV infection

• Blood samples

- For full blood count for MLR calculation
- For transaminases and C-reactive protein
- For CD4 cells count
- For biobanking (storage of frozen samples)

• Imaging exams

- Abdominal ultrasonography to assess the presence of intra-abdominal lymphadenopathies included as one item of the PAANTHER TB treatment decision algorithm, and additional signs such as hepatomegaly, splenic or hepatic micro-abscesses, pericardial/pleural effusion, and/or ascites
- Chest X-ray: standard anteroposterior and lateral view in children aged ≤ 5 years; standard anteroposterior view in children aged > 5 years

• Bacteriological specimen collection:

Initial bacteriological specimen collection will be done as soon as possible and within 3 days of inclusion, including:

- 1 NPA, collected by the nurse on the day of admission without prior nasal instillation (see Appendix 4)
- 1 stool sample, collected as soon as the child is able to produce stool
- 2 GAs or 2 expectorated sputum samples in children who are able to expectorate

The tolerability, feasibility, and adverse events linked to NPA specimen collection will be assessed by study nurses using qualitative and quantitative tools (Cf § 7.8 and 9.2).

Bacteriological tests performed on collected specimen are detailed in § 8.2.

Additionally, a urine sample will be collected for biobanking.

Extra tests not planned by the protocol will be requested by the clinician in accordance with local practice and the national recommendations.

7.5. TB treatment decision using the algorithm

As soon as possible and during clinical, biological and radiological investigations, the clinician will make a diagnosis according to the PAANTHER TB-treatment decision algorithm (see Figure 1). Alternative diagnoses will be collected. The diagnosis visit is expected at the latest at day 1 or 2.

A flexibility to start TB treatment in children with a score <100 will be allowed in case of severe/life threatening condition. Children without such conditions not started on TB treatment will be reevaluated at the day 7 visit.

7.6. Treatments

• TB treatment initiation

TB treatment using 2HRZ(E)/4RH with new paediatric formulations according to National Guidelines will be initiated in children with a score≥100. Children with rifampicin resistance detected by Ultra will have culture and phenotypic drug sensibility testing (DST) performed on leftovers from NPAs and stool (and additional samples if needed), and will be started on empirical MDR-TB treatment. Arrangements will be made with NTPs for fast-track MDR-TB treatment initiation.

• Isoniazid Preventive Therapy

As recommended per WHO 2011 "Guidelines for intensified tuberculosis case-finding and isoniazid preventive therapy for people living with HIV in resource-constrained settings", children not initiated on treatment as per PAANTHER TB-treatment decision algorithm will be initiated as soon as possible on IPT or an alternative treatment for latent TB infection (LTBI), such as 3RH [65], as locally available in-country.

• Evaluation of adherence

Adherence to the TB treatment will be evaluated by pill count except in case of Directly Observed Therapy.

• Antiretroviral treatment

ART will be started following national recommendations. As recommended by WHO, this should be done within 2 to 8 weeks of TB treatment initiation in children diagnosed with TB, and not later than 2 weeks in children with CD4 count below 50 cells/µL [66]. In children already on ART, a change of antiretroviral regimen will be considered if appropriate (e.g. switch from nevirapine or lopinavir to efavirenz, or double boosting of lopinavir if possible in accordance with National Guidelines).

• Associated treatments

Prophylactic treatments for opportunistic infections (Cotrimoxazole +/- Fluconazole) may be prescribed according to the recommendations of national programs, as well as Isoniazid prophylaxis in case TB diagnosis is ruled out by the clinician.

• Treatment dispensing

Anti-tuberculosis and antiretroviral drugs will be provided by national authorities. They will be dispensed in accordance with each hospital's procedures. Their access will be free of charge for patients in accordance with the recommendations of national protocols.

7.7. Follow-up

All children will be followed-up for 6 months upon enrolment, with systematic study visits at day 15, month 1, 2, 3, and 6. In children not initiated on TB treatment as per the PAANTHER treatment decision algorithm, an extra visit will be performed at day 7 for an early detection of missed TB cases. The dates of each visit must comply with the provisional patient schedule generated from the date of inclusion of the child. For month 1 to month 6 visits, a flexibility of +/- 2 weeks around theoretical dates of protocol visits will be allowed to enable study visit to coincide with routine ART and HIV follow-up visits. If a child fails to attend a study follow-up visit, the clinical team on site will confidentially contact the parent(s)/guardian(s) and encourage/assist them to bring back the children for follow-up.

Each visit will comprise:

- Clinical evaluation: complete physical examination, vital signs, nutritional status
- Medical history since the last visit: any new clinical and AE with special attention to drug tolerance and TB paradoxical reaction
- CXR to detect new or aggravated lesions (at M2 and M6 final visit)
- Laboratory assessment: CBC, transaminases and CRP at M2 and M6 visit, CD4 count at M6 visit
- Evaluation of adherence to TB treatment, if initiated
- Any change of ART occurring during the study follow-up
- Study drug prescription and dispensation to cover time to the next follow-up visit

In case of TB treatment failure or unfavourable evolution, appropriate samples will be performed and resistance to TB drugs will be assessed using methods available on sites (phenotypic DST or line probe assays).

In children not initially diagnosed with TB, who show no clinical improvement or present additional signs of presumptive TB at day 7, 15, M1, M2, or M3, bacteriological specimen collection and Ultra testing will be repeated. These will include standard samples, i.e. GA or expectorated sputum. CXR could also be repeated, in addition to M2 and M6 visits, for children with clinical signs suggestive of TB at other scheduled or unscheduled study visit.

During the last follow-up visit at month 6, an assessment of the TB disease evolution and response to treatment will be made (cured, treatment failure, continuation of TB treatment, death, lost to follow-up).

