7.11. Final study visit

For each enrolled child, the last protocol visit will occur 6 months after inclusion. Once completed the 6-month follow-up period, children will continue to benefit from regular treatment and care provided by National Programs.

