7.13. Post-study care conditions

At the end of the study, children will continue to receive care and treatment according to the conditions defined by their country authorities. Children with ongoing TB treatment at M6 will be followed-up and treated under the responsibility of NTPs. Until the ongoing TB episode is cured, the study investigators, in close collaboration with NTPs, will actively contribute to facilitate their access to the best available TB disease management.

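### Treatment outcome (part of secondary endpoint 4) is read at a Month 6 visit that may precede the end of the 2+4 month course, so an on-schedule course and a prolonged one share a label

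*Protocol*

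**What the plan says.** Four parts of the protocol meet here.

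- **Where the outcome is read.** Section 7.7: "During the last follow-up visit at month 6, an assessment of the TB disease evolution and response to treatment will be made". The categories listed are cure, failure, continuation, death and loss to follow-up. There is no category for a completed course and none for a course not yet due to end.
- **How the visit is dated.** Section 7.7: "The dates of each visit must comply with the provisional patient schedule generated from the date of inclusion of the child". It adds: "For month 1 to month 6 visits, a flexibility of +/- 2 weeks around theoretical dates of protocol visits will be allowed". The stated purpose of the window is to fit study visits to routine HIV appointments. Section 7.11 confirms that "the last protocol visit will occur 6 months after inclusion".
- **How long the course runs and when it starts.** Section 7.6: "TB treatment using 2HRZ(E)/4RH with new paediatric formulations according to National Guidelines will be initiated". That is 2+4 months. On the start, section 7.5 says: "The diagnosis visit is expected at the latest at day 1 or 2". The schedule in section 7.3 likewise places algorithm scoring at D0 and D1-D2.
- **What happens if treatment is still running.** Section 7.13: "Children with ongoing TB treatment at M6 will be followed-up and treated under the responsibility of NTPs". No later outcome is collected for the study.

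The outcome serves secondary objective 4 (children initiated on treatment as per the algorithm) and secondary endpoint 4 (children on TB treatment).

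**The concern.** The clock for the visit starts at inclusion and has an early side. The clock for the course starts at treatment and has none. A child can therefore attend a fully compliant Month 6 visit while a normally running course still has days or weeks to go.

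If that child is responding, the only label that fits is continuation. A child whose treatment was lengthened because of poor response gets the same label. One category then holds two opposite clinical meanings, and which children enter it depends on the appointment date. Because the window is there to match routine clinic calendars, the mix could also differ by site or country for reasons unrelated to treatment. Since the study stops at that visit, the outcome at the end of the course is never observed for these children.

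**Working it through.** The protocol states no share of children still on treatment at Month 6, so there is no figure to reproduce. The check is how large that share could be.

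**Inputs**
- V, nominal Month 6 day counted from inclusion (7.7, 7.11). Not given in days; 180-183 assumed.
- Window: V - 14 to V + 14 days (7.3, 7.7).
- s, start of treatment: day 0 to 2 (7.3, 7.5).
- L, course length: 2+4 months (7.6). Not given in days. Main assumption: the same six months as the visit, L = V. Alternative: 24 weeks, L = 168.
- Distribution of visit dates in the window: not stated, so it must be assumed.

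**Formula.** A child is unfinished if the visit day is earlier than L + s. With visits uniform over the 28 days, the share is (L + s - V + 14)/28, cut to lie between 0 and 1.

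**Six-month course (L = V), uniform visits**
- s = 0: 14/28 = 50%
- s = 1: 15/28 = 54%
- s = 2: 16/28 = 57%

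**Six-month course, visits clustered** (normal, cut to the window, SD 3 to 7 days; ranges cover s = 0 to 2)

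| Mean visit day | Share unfinished |
|---|---|
| 7 days early | 81% to 99.9% |
| on the nominal day | 50% (s = 0); 62% to 75% (s = 2) |
| 7 days late | 1% to 28% |

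**24-week course, uniform visits**
- V = 180: (168 + s - 180 + 14)/28 = 2/28 = 7% (s = 0) to 4/28 = 14% (s = 2)
- V = 183: 0% (s = 0) to 1/28 = 4% (s = 2)
- Overall, 0% to 14%

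**A later start.** D0-D2 is an expectation. Section 1 reports a median of 7 days (IQR 5 to 11) to treatment in the study that developed the algorithm. With L = V and uniform visits, s = 7 gives 21/28 = 75%, and s = 5 and s = 11 give 19/28 = 68% and 25/28 = 89%. The algorithm is meant to shorten that delay, so these are sensitivity figures only.

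**After a change**
- Outcome read on or after each child's own end date: 0% unfinished because of visit timing.
- Inclusion anchor kept, with only 0 to +14 days allowed and uniform visits: s/14, which is 0% (s = 0) to 2/14 = 14% (s = 2).

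**The case against.** The strongest reply is that this was foreseen. Continuation is a listed category, section 7.13 provides for children still on treatment, and a 6-month follow-up is stated consistently. On this view it is a deliberate limit. That stands as far as it goes: ongoing treatment at Month 6 was not overlooked. But a foreseen category that mixes on-schedule with prolonged courses is still uninterpretable.

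A second reply is that section 11.2.3 leaves the detail of secondary endpoints to the analysis plan, which could split the category by treatment dates. That also stands in part, for the labels. No analysis plan can recover an end-of-course outcome that was never collected.

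A third reply is that section 7.7 speaks of disease evolution and response, which can be judged shortly before a course ends. This is fair, and it is why weight gain, symptom resolution and failure remain readable. It does not say how a responding child seen early should be classified.

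Several stronger readings are tempting and are not supported:

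- **That about half of treated children cannot have finished.** This needs symmetric visit dates and a course exactly as long as the nominal Month 6. The documents state neither.
- **That 176 to 201 children are affected.** This takes 50% to 57% of 352, the planned treated number at section 4.3's figures (0.5 x 0.89 + 0.5 x 0.39 = 0.64; 0.64 x 550 = 352). Children who die, withdraw or are lost have no Month 6 visit to mistime, and 550 already includes a 10% allowance for missing data.
- **That missed cases add to the count.** Objective 4 covers only children treated as per the algorithm. Nor is non-completion certain for every late start: with L = V, a start at day 7 ends at V + 7, inside the window. It is certain only for starts after day 14.
- **That MDR-TB courses cannot finish by Month 6.** The protocol gives no length for that treatment.
- **That objective 4 cannot be answered.** Only one component is blurred.

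**Conclusion.** The timing conflict is real and confined to the treatment-outcome component of secondary endpoint 4. Followed as written, the protocol lets the category of a responding child turn on the date of the appointment, and it collects nothing afterwards to settle the matter.

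The size cannot be fixed from the documents. Across the readings tried it runs from about 0% to nearly 100% of treated children who attend Month 6. The 50% to 57% figure holds only for a six-calendar-month course, a start at D0-D2 and visits uniform in the window. The effect is small only if visits tend to run late or the course is counted as 24 weeks.

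The primary endpoint is not touched, since it concerns children not started on treatment. This should be corrected, but it does not threaten the main result.

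**What to change.** Reconcile sections 7.5 to 7.7 with section 7.13, leaving every treatment rule as it is.

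1. For children initiated on treatment as per the algorithm, read the treatment outcome at a Month 6 visit held on or after the child's own planned end-of-course date, for example by opening the visit window on that date. With a six-month course and a start at D0-D2, that date is V to V + 2, so 12 to 14 days of the present window remain.
2. Where treatment is still running at the last visit, use the recorded start date to report *course on schedule, not yet evaluable* separately from *extended beyond planned course*. Make sure the start date is captured; section 10.1.1 lists TB treatment data without naming it.
3. Where available, take the end-of-treatment outcome for these children from the national programme record.
4. State whether endpoint 4 covers only algorithm-treated children, as objective 4 does, or all children on TB treatment.

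The cost is slightly later Month 6 visits in treated children, some loss of freedom to match routine appointments, two category labels and, if step 3 is used, a small amount of record abstraction.
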